1.27 Special Concerns for the Use of Raltegravir in the Neonate

UGT1A1, the enzyme primarily responsible for raltegravir metabolism, is also the only enzyme that contributes to bilirubin glucuronidation in human hepatocytes, and as such is essential for the biliary elimination of bilirubin from the body [48]. Glucuronidation activity is low in fetuses and in the newborn immediately after birth but increases exponentially over the first weeks and months of life. Hepatic UGT activity in liver samples is very low in samples from 2nd trimester fetuses, and increases roughly 10 fold during the 3rd trimester and then another 100-fold during the first 3 months following a full term delivery [49]. The low level of hepatic UGT activity at birth plays a major role in the elevations of bilirubin routinely seen in the newborn, referred to as physiologic jaundice.

In adults, decreased UGT1A1 activity has been shown to result in increased plasma concentrations of both bilirubin and raltegravir. Atazanavir, an HIV protease inhibitor, is also an inhibitor of UGT1A1 and elevation of direct bilirubin is a very common side effect of atazanavir use in HIV infected adults. When raltegravir and atazanavir are co-administered, raltegravir AUC increases on average by 41% and C_{max} by 77% [50]. Similarly, the *UGT1A1* *28/*28 genotype, one of the common genotypes found in individuals with Gilbert's Syndrome, is characterized by a roughly 30% decrease in UGT1A1 activity and increased serum bilirubin concentrations [51, 52]. Following standard dosing with raltegravir, individuals with the *UGT1A1* *28/*28 genotype have on average an increase of 40% in raltegravir AUC and C_{max} and of 90% in trough concentration compared to individuals with wild type *UGT1A1*. Raltegravir elimination $t_{1/2}$ was not prolonged in the *UGT1A1* *28/*28 individuals, suggesting that increased raltegravir bioavailability due to decreased hepatic first pass metabolism may play a major role in the increase in raltegravir plasma concentrations seen in these individuals [53].

Administration of an exogenous drug that is eliminated by glucuronidation poses special risks in the newborn. Low UGT activity that results in decreased elimination of endogenous bilirubin and physiologic jaundice will also result in decreased metabolism

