2.2 Secondary Objectives

- 2.21 To assess safety and tolerability of raltegravir oral granules for suspension through 24 weeks of life when administered during the first 6 weeks of life with standard PMTCT ARV prophylaxis to infants exposed to HIV-1 assessed at risk of infection.
- 2.22 To investigate the relationship between neonatal raltegravir elimination and UGT1A1 genotype and whether there is an association of UGT1A1 (*28/*28) and SLC01B3 (rs2117032-C/T) with hyperbilirubinemia.

[figure not shown]

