8.2 Outcome Measures

(Outcome Measures are for infants only; maternal data are to be used as covariates, not as outcomes)

8.21 Primary Endpoints for Cohorts 1 and 2

Toxicity Endpoints: Toxicity from study entry through 6 weeks of life

- Adverse events of Grade 3 or 4 severity or death (primary safety endpoint for final analysis)
- Suspected adverse drug reaction (SADR) of Grade 3 or 4 severity or death (primary safety endpoint for dose finding guidelines described in Section 8.52) but secondary safety endpoint for the analyses described in Section 8.71)

Pharmacokinetic Endpoints: (See Section 9.0: Clinical Pharmacology Plan)

8.22 Primary Response Variables for Cohorts 1 and 2 Pharmacokinetic parameters (See Section 9.0)

8.23 Secondary toxicity endpoints for Cohorts 1 and 2: Toxicity from study entry weeks through 24 weeks of age

- Adverse events of Grade 3 or 4 severity or death
- Suspected adverse drug reaction (SADR) of Grade 3 or 4 severity or death

8.24 Secondary Response Variables for Cohorts 1 and 2

- UGT1A1 genotype (presence or absence of *28/*28 genetic variant)
- SLCO1B3 (rs2117032-C/T) genotype
- Hyperbilirubinemia defined as total bilirubin exceeding 16.0 mg/dL or infant receiving phototherapy, or transfusion therapy, or other therapies for hyperbilirubinemia

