To assess the safety and tolerability of RAL through 24 weeks of life, descriptive statistics will be calculated summarizing the proportion of infants who had an adverse event of Grade 3 or 4 severity or death based on safety data from study entry through 24 weeks of age on all safety evaluable infants in each of the four study groups. A similar analysis will be done to summarize proportion of infants who had an SADR of Grade 3 or 4 severity or death.

To investigate the relationship between neonatal raltegravir elimination and UGT1A-1 genotype, participants will be divided into subgroups, based on whether or not they exhibit polymorphisms on UGT1A-1. Descriptive analyses will be performed to compare these subgroups with respect to measures of central tendency and dispersion for raltegravir AUC.

Similar descriptive analyses will also be performed to investigate the association of UGT1A1 (*28/*28) and SLCO1B3 (rs2117032-C/T) with hyperbilirubinemia. If the sample size and the data distributions make this possible, a logistic regression model predicting for probability of neonatal hyperbilirubinemia with UGT1A1 (*28/*28) genotype, SLCO1B3 (rs2117032-C/T) genotype, gestational age and gender as predictors will be fitted on the pooled data across the two cohorts. Note that the sample size may be too small and/or there may be insufficient cases of hyperbilirubinemia to make this possible. If this analysis can be done, it will have minimal power, but the size and directionality of effects will be compared with those predicted on the basis of previous findings.

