4.9 Genotype Analysis

Purpose:

To list the tables for investigating the relationship between neonatal RAL elimination (as reflected in CL/F) and UGT1A-1 genotype, and the relationship between UGT1A-1 and SLCO1B3 with hyperbilirubinemia.

Analysis Program Validation:

Code review required.

Data:

HUMGENO table and LBW0093 CRF (TBILCV, BILPHOTO, BILTRANS, BILOTH and BILOTHSP).

Analysis:

- a) Response variables for genotype analysis:
 - UGT1A-1 genotype (presence or absence of *28/*28 genetic variant):
Wild-type: (TA)₆(TA)₆; mutation: (TA)₅(TA)₆, (TA)₆(TA)₇ and (TA)₇(TA)₇
 - SLCO1B3 (rs2117032-C/T) genotype:
C/C, C/T and T/T
 - Hyperbilirubinemia defined as total bilirubin exceeding 16.0 mg/dL or infant requiring exchange transfusion for hyperbilirubinemia

b) Output tables:

Table: Summary descriptive statistics (N, geometric mean, median, 25th and 75th percentiles, min, and max) on CL/F will be generated for the subgroups of participants depending on whether they exhibit the UGT1A1 polymorphism.

Table 8: Summary of Infant RAL CL/F between UGT1A1 Genotype Groups for Cohort 1 (mock-up table)

		UGT1A1 Genotypes					Overall	p-value ^a for all genotypes	p-value ^b for wild-type vs. mutation
		Wild-type	Mutation			Overall			
		(TA)6(TA)6	(TA)5(TA)6	(TA)6(TA)7	(TA)7(TA)7				
CL/F of RAL-naïve Infants	N								
	mean								
	median								
	...								
CL/F of RAL-Exposed Infants	N								
	mean								
	median								
	...								
CL/F of All Infants	N								
	mean								
	median								
	...								

a Comparison of median among different genotypes will use Kruskal–Wallis test for CL/F of all infants only. The formal comparison will be done only if we have enough infants in the listed genotype groups.

b Comparison of median between wild-type vs. mutation will use Wilcoxon Rank Sum Test for CL/F of all infants only. The formal comparison will be done only if we have enough infants in the listed genotype groups.

**Table 9: Summary of Infant RAL CL/F between UGT1A1 Genotype Groups for Cohort 2
(mock-up table)**

		UGT1A1 Genotypes					Overall
		Wild-type	Mutation			Overall	
		(TA)6(TA)6	(TA)5(TA)6	(TA)6(TA)7	(TA)7(TA)7		
CL/F from the 1st intensive PK analysis	N						
	mean						
	median						
	...						
CL/F from the 2nd intensive PK analysis	N						
	mean						
	median						
	...						

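### SAP 4.9 labels its UGT1A1 variable as *28/*28 but codes it as any listed variant, so none of its hyperbilirubinemia tests isolates the *28/*28 genotype that the protocol names

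*SAP*

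**What the plan says.** The hyperbilirubinemia part of Protocol objective 2.22 asks "whether there is an association of UGT1A1 (*28/*28) and SLC01B3 (rs2117032-C/T) with hyperbilirubinemia". Protocol 8.24 lists the corresponding response variable as "UGT1A1 genotype (presence or absence of *28/*28 genetic variant". Protocol 8.711 carries the same genotype into the hyperbilirubinemia analysis and, if the data allow it, into a logistic model for the "probability of neonatal hyperbilirubinemia with UGT1A1 (*28/*28) genotype, SLCO1B3 (rs2117032-C/T) genotype, gestational age and gender as predictors".

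For raltegravir elimination the protocol is broader. Objective 2.22 refers only to UGT1A1 genotype, and 8.711 says "participants will be divided into subgroups, based on whether or not they exhibit polymorphisms on UGT1A-1".

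SAP 4.9 uses one variable for both questions. It labels it "UGT1A-1 genotype (presence or absence of *28/*28 genetic variant" and codes it on the next line as "Wild-type: (TA)₆(TA)₆; mutation: (TA)₅(TA)₆, (TA)₆(TA)₇ and (TA)₇(TA)₇". The tests are:

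- CL/F, Table 8: a Kruskal-Wallis test across all genotypes and a two-group test, of which the footnote says "Comparison of median between wild-type vs. mutation will use Wilcoxon Rank Sum Test for CL/F of all infants only".
- CL/F, Table 9 (Cohort 2): no p-values yet; formal comparisons wait for the RAL-exposed group.
- Hyperbilirubinemia, Table 10 (Cohort 1) and a similar Cohort 2 table: Fisher's exact test across all genotypes, and Fisher's exact test for wild-type against mutation.

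**The concern.** The label and the coding describe different exposures. *28/*28 is a single homozygous genotype, whereas the mutation group pools three genotypes, two of them heterozygous. The label says that the *28/*28 question is being addressed, but the two-group comparison is of carriers of any listed variant against (TA)6(TA)6.

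This matters most for hyperbilirubinemia, where the protocol names *28/*28. Its biological rationale is also given for that genotype: Protocol 1.27 says *28/*28 "is characterized by a roughly 30% decrease in UGT1A1 activity and increased serum bilirubin concentrations". At stake is a secondary objective that would be reported without the contrast it specifies, and a two-group p-value that could be read as answering a question it does not address.

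**Working it through.** The documents state no sample size, power or effect size for the genotype tests, so there is no plan figure to reproduce. The check is one of definitions, followed by an illustration.

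**Step 1: which coded genotypes can be *28/*28?** The documents do not say which TA repeat is *28. The answer does not need that mapping. A *28/*28 infant has two copies of the same allele. (TA)5(TA)6 and (TA)6(TA)7 each have two different alleles, so neither qualifies under any mapping. (TA)6(TA)6 is called wild-type. Of the four listed genotypes only (TA)7(TA)7 is left, so it is presumably *28/*28. (TA)5(TA)6 contains no (TA)7 allele at all.

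**Step 2: protocol against SAP, by outcome.**

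| Outcome | Protocol exposure | SAP two-group coding | Match? |
|---|---|---|---|
| Hyperbilirubinemia | *28/*28 (2.22, 8.24, 8.711) | any listed variant vs (TA)6(TA)6 | No |
| RAL elimination (CL/F) | UGT1A1 genotype (2.22); any polymorphism, yes or no (8.711) | any listed variant vs (TA)6(TA)6 | Yes with 8.711; no with 8.24 or the SAP label |

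**Step 3: does another test in SAP 4.9 isolate *28/*28?** The all-genotype Fisher test is unordered over four groups. A small p-value would not say which genotype differs, and a large one would not rule out a difference confined to (TA)7(TA)7. So no test in SAP 4.9 contrasts *28/*28 with the rest.

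**Step 4: how mixed could the mutation group be?** This is an illustration only. Assumptions that are not in the documents: Hardy-Weinberg proportions, no (TA)5 allele, (TA)7 allele frequency q from 0.2 to 0.5, and every infant genotyped (Protocol 3.2 makes genotyping optional). Cohort 1 has 10 + 6 = 16 infants (SAP 2). Cohort 2 has 26 RAL-naïve (SAP 2) plus a minimum of 8 RAL-exposed (Protocol 8.4), that is 34.

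Share of homozygotes in the mutation group = q²/(1 − (1 − q)²) = q/(2 − q). Expected homozygotes = n × q². If hyperbilirubinemia risk were 50% in homozygotes and 10% in everyone else (assumed), the risk in the mutation group would be 0.10 + 0.40 × share.

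| q | Homozygote share | Expected, n = 16 | Expected, n = 34 | Mutation-group risk (wild-type 10%) |
|---|---|---|---|---|
| 0.2 | 11% | 0.6 | 1.4 | 14% |
| 0.3 | 18% | 1.4 | 3.1 | 17% |
| 0.4 | 25% | 2.6 | 5.4 | 20% |
| 0.5 | 33% | 4.0 | 8.5 | 23% |

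A simulation on the same assumptions (2,000 replicates, two-sided 0.05) gave these Fisher powers for the SAP split against homozygotes versus the rest. At n = 16: 1% against 8% (q = 0.3) and 1% against 17% (q = 0.4). At n = 34: 4% against 29% and 3% against 45%. These gains depend on heterozygotes having no effect, which the documents do not say.

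**The case against.** **CL/F.** A reader might infer that the CL/F comparison is wrong as well and should be replaced by *28/*28 against the rest. The documents do not support that. Protocol 8.711 prescribes a split on any polymorphism for elimination, and Protocol 3.2 cites *28/*28 only as an example. Nor would a replacement clearly be better. Protocol 1.27 gives a 40% higher AUC in *28/*28 individuals, in a passage about adults. If heterozygotes carry half that effect on the log scale, the SAP split would show 1.4^(0.5 + 0.5 × share) = 1.21, 1.22, 1.23, 1.25 for q = 0.2, 0.3, 0.4, 0.5. Homozygotes against the rest would show 1.4^(1/(1 + q)) = 1.32, 1.30, 1.27, 1.25, because heterozygotes now dilute the comparator, and with a smaller group. In simulations at n = 34, q = 0.3 and a CV of 40% (the AUC figure for 4 weeks to under 6 months in Protocol Table 4), Wilcoxon power for the homozygote split against the SAP split was 23% against 6% with no heterozygote effect, but 14% against 27% with a half effect. This objection stands in full.

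**The data remain visible.** Tables 8 to 10 give each genotype its own column, so (TA)7(TA)7 infants and (TA)5 carriers can be seen separately. That stands, and it limits the harm to the missing contrast and the label.

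**The protocol's logistic model.** Section 8.711 names *28/*28 as a predictor, so the question could still be tested there. But that model depends on the data permitting it, SAP 4.9 does not set it out, and it would inherit the broad coding if built from the SAP's definition.

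**Low stakes.** The objective is secondary, the SAP itself warns of very low power, and no dose or safety rule uses genotype. At n = 16 and q = 0.2, the chance of no homozygote at all is 0.96^16 = 0.52. This caps the importance of the point, but it is not a reason to test a different exposure from the one named.

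**Conclusion.** The point holds for hyperbilirubinemia. The SAP's two-group Fisher test uses an exposure other than the one in Protocol 2.22, 8.24 and 8.711, and no other test in SAP 4.9 isolates *28/*28. That conclusion rests only on the SAP's own notation. For CL/F the split follows Protocol 8.711, and the fault is confined to the SAP label and its mismatch with 8.24.

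Two stronger readings should be resisted. One is that the tables would present a mutation effect as the *28/*28 result. The p-value columns are headed as wild-type against mutation and the component genotypes are listed, so the tables themselves do not make that claim. The other is that a *28/*28 effect would be diluted by a known amount. The size of any dilution depends on allele frequency and on the effect in heterozygotes, neither of which is in the documents; the figures above show a range under assumptions and are not estimates for this trial.

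The consequence is modest, but the mismatch is clear and correcting it is nearly free.

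**What to change.** In SAP 4.9:

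- State which TA genotype is *28/*28 (presumably (TA)7(TA)7; the study team should confirm) and define the Protocol 8.24 variable as that genotype against all others.
- Add a Fisher comparison of *28/*28 with all other genotypes for hyperbilirubinemia to Table 10 and to the Cohort 2 table.
- Do not count (TA)5(TA)6 as *28; keep it in its own column.
- Keep the two-group split for CL/F, relabelled as (TA)6(TA)6 against any listed UGT1A1 variant. A *28/*28 contrast or a trend by number of (TA)7 alleles could be added as support, and the deferred Cohort 2 comparisons in Table 9 could be specified at the same time.

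The cost is SAP wording and table shells; no new data are needed. The drawback is that very few homozygotes are likely, so the added comparison will be imprecise and may not be possible in Cohort 1. The SAP should say that counts alone will be reported in that case.

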6.13 Bilirubin Management

Due to the potential for interactions between RAL and bilirubin affecting RAL pharmacokinetics and bilirubin elimination and toxicity (see Section 1.27) special management procedures for bilirubin will be used. Bilirubin concentrations and interventions to lower bilirubin (such as phototherapy and exchange transfusion) will be recorded but bilirubin will be graded according to the DAIDS Toxicity Table and

managed according to the schema described below. Hyperbilirubinemia will be managed by clinical caregivers according to local standards of care. If total bilirubin is >16.0 mg/dL or an exchange transfusion is performed, no further RAL doses will be administered but participants will continue to be followed for safety assessments. Participants who receive phototherapy may continue to receive study drug as long as total bilirubin concentration \leq 16.0 mg/dL.

The protocol team must be notified if study drug is held due to elevated bilirubin or of Grade 3 or 4 hyperbilirubinemia determined to be at least possibly related within 24 hours of site awareness at [contact].

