This is a Phase I multi-center, open label, non-comparative study to evaluate the safety and pharmacokinetics (PK) of raltegravir (RAL) administered to HIV-1-exposed full-term (≥ 37 weeks of gestation) neonates at high risk of acquiring HIV-1 infection. The goal is to determine the appropriate dosing regimen of RAL oral granules for suspension that can be safely administered to neonates and infants in the first 6 weeks of life.

This study will enroll approximately 50 neonates in order to accrue a minimum of 32 PK evaluable high risk HIV-1-exposed neonates and their mothers across Cohort 1 and Cohort 2. Mother-infant (M-I) pairs will enroll at the time of delivery up to 48 hours of life, which is the latest time for administration of first neonatal RAL dose. Cohort 1 opened first and accrual to Cohort 2 was contingent upon neonates enrolled in Cohort 1 successfully meeting safety criteria and providing adequate PK data so that the dosing regimen was developed for daily dosing through 6 weeks of age for Cohort 2. Through Protocol Version 1.0 LoA #2 Cohort 2 RAL-naïve group was opened to accrual with the following dosage: 1.5 mg/kg once daily during Days 1-7 of life, 3.0 mg/kg twice daily during Days 8-28 of life, and 6.0 mg/kg twice daily during Days 29-42 of life.

At the time of this SAP update, Cohort 1 (both RAL-naïve and RAL-exposed groups) is closed to accrual and follow-up and Cohort 2 RAL-naïve group is closed to accrual but follow-up is ongoing. The final accrual numbers are 10 M-I pairs for Cohort 1 RAL-naïve, 6 M-I pairs for Cohort 1 RAL-exposed, and 26 M-I pairs for Cohort 2 RAL-naïve groups under protocol Version 1.0. The team estimated that the study will take 3 years to fully accrue under protocol

Version 1.0. Protocol Version 2.0 is currently being drafted and if approved, will open accrual to Cohort 2 RAL exposed group.

PK evaluable infants are those whose PK results provide data on the primary PK parameters of interest. If a participant has unevaluable PK data, which reflects uncertainty about appropriate exposure to the study medication, the participant will be excluded from PK analyses and will be replaced. PK analyses will be done by the protocol pharmacologist.

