secondary safety endpoints for final analysis)

Note: Summary tables will include statistics for infant subgroups and overall and listing will include information on infant in utero RAL exposure and RAL dosing.

Table: Summary tables showing number (%) and the 2-sided 90% confidence interval (CI) using the Clopper-Pearson exact method estimates of the proportion of infants meeting the primary and secondary safety endpoints(will provide as footnote number of infants with missing data). The primary analysis will be on the primary safety endpoint.

Table 6: Proportion of Infants Meeting the Primary Safety Endpoint (mock-up table)

RAL-naïve			RAL-exposed	Overall
3mg/kg-3mg/kg	2mg/kg- 3mg/kg	Overall	1.5mg/kg-3mg/kg	
N (%) [90% CI]	N (%) [90% CI]	N (%) [90% CI]	N (%) [90% CI]	N (%) [90% CI]

Note: Similar table will be generated for Cohort 2 with appropriate column labels appropriate for Cohort 2 subgroups of infants.

Table: Summary tables of worst adverse events (laboratory, signs/symptoms and diagnoses) for each of the primary and secondary safety endpoint.

Table: Summary of worst grade baseline events (laboratory, signs/symptoms and diagnoses).

Table: Listing of reasons for infant death and age (weeks) at death.

Table: Summary table showing number (%) and the 2-sided 90% confidence interval (CI) using the Clopper-Pearson exact method estimates of the proportion of infants who had total bilirubin exceeding 16.0 mg/dL, or received phototherapy, transfusion therapy or other therapies for hyperbilirubinemia.

The following SDAC internal listings will be generated to facilitate the write-up of the SDAC final report. The listings will also be provided to the manuscript writing team. SDAC public IDs will be used and no identifying dates will be provided.

- a. Per infant listings of baseline events, AEs and SADRs with site and team assessment of drug attribution.
- b. Per infant listing of ARVs from TXW0276 and PE0421.

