Note: This table is for Cohort 2 RAL-naïve group only and should we have data on Cohort 2 RAL-exposed group, additional columns for: (i) RAL-exposed group, and (ii) Overall Cohort 2, will be added. Formal comparisons for all Cohort 2 infants will be done by then.

Table: Association between UGT1A-1 genotypes and hyperbilirubinemia (yes/no) with Fisher’s Exact Test.

Table 10: Summary of Cohort 1 Infant Hyperbilirubinemia between UGT1A1 Genotype Groups (mock-up table)

Characteristic		Wild-type	Mutation				Overall (N=0)	P-value* for all genotype groups	P-value* for Wild-type vs. Mutation
		(TA)6(TA)6	(TA)5(TA)6	(TA)6(TA)7	(TA)7(TA)7	Overall			
Hyperbilirubinemia	Yes	0	0	0	0	0	0.000	0.000	
	No	0	0	0	0	0			

*Fisher’s Exact Test. The power of test will depend upon the distributions of the variables to be analyzed, but will be extremely limited due to the small sample size.
Note: Similar table will be created for Cohort 2 infants.

Table: Association between SLCO1B3 genotypes and hyperbilirubinemia (yes/no) with Fisher’s Exact Test.

Table 11: Summary of Cohort 1 Infant Hyperbilirubinemia among SLCO1B3 Genotype Groups (mock-up table)

Characteristic		C/C (N=0)	C/T (N=0)	T/T (N=0)	Total (N=0)	P-Value*
Hyperbilirubinemia	Yes	0	0	0	0	0.000
	No	0	0	0	0	

*Fisher’s Exact Test. The power of test will depend upon the distributions of the variables to be analyzed, but will be extremely limited due to the small sample size.
Note: Similar table will be created for Cohort 2 infants.

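### The SAP's genotype tables define hyperbilirubinemia more narrowly than protocol 8.24, without explanation, so infants treated by phototherapy or another therapy alone count as non-cases

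*SAP*

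**What the plan says.** Protocol 8.24 lists the outcome among the secondary response variables for both cohorts: "Hyperbilirubinemia defined as total bilirubin exceeding 16.0 mg/dL or infant receiving phototherapy, or transfusion therapy, or other therapies for hyperbilirubinemia". It serves objective 2.22, which asks whether UGT1A1 and SLCO1B3 variants are associated with hyperbilirubinemia.

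SAP 4.6 plans a safety table giving the proportion, with a 90% exact interval, of "infants who had total bilirubin exceeding 16.0 mg/dL, or received phototherapy, transfusion therapy or other therapies for hyperbilirubinemia". Its components are those of 8.24.

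SAP 4.9, under response variables for the genotype analysis, has instead "Hyperbilirubinemia defined as total bilirubin exceeding 16.0 mg/dL or infant requiring exchange transfusion for hyperbilirubinemia". This is the variable that enters Table 10 ("Association between UGT1A-1 genotypes and hyperbilirubinemia (yes/no) with" Fisher's exact test), Table 11 for SLCO1B3, and their Cohort 2 counterparts. Yet the data line of the same section reads "HUMGENO table and LBW0093 CRF (TBILCV, BILPHOTO, BILTRANS, BILOTH and BILOTHSP", which includes fields that the definition does not use.

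On management, protocol 6.13 states that "Hyperbilirubinemia will be managed by clinical caregivers according to local standards of care". It also states that "Participants who receive phototherapy may continue to receive study drug as long as total bilirubin concentration" is no higher than 16.0 mg/dL.

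**The concern.** The narrower wording drops two of the four routes by which an infant becomes a case under the protocol: phototherapy and other therapies. The SAP does not say why. The route most likely to matter is one that the protocol itself anticipates, because 6.13 leaves treatment to local practice and describes infants on phototherapy whose bilirubin has not exceeded 16.0 mg/dL.

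At stake is whether the analysis answers the secondary objective with the outcome the protocol defined for it. A reader of the final report could also find an infant counted in the SAP 4.6 bilirubin table and placed in the no-hyperbilirubinemia row of the genotype tables, with nothing to explain the difference.

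**Working it through.** **Step 1. Set the three texts side by side.**

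| Component | Protocol 8.24 | SAP 4.6 table | SAP 4.9 |
|---|---|---|---|
| Total bilirubin >16.0 mg/dL | counted | counted | counted |
| Phototherapy | counted | counted | not counted |
| Transfusion | transfusion therapy | transfusion therapy | exchange transfusion only |
| Other therapies | counted | counted | not counted |

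SAP 4.6 and SAP 4.9 list the same five LBW0093 fields. Going by their names (the SAP gives no data dictionary), the SAP 4.9 definition needs TBILCV and BILTRANS and leaves BILPHOTO, BILOTH and BILOTHSP unused. A smaller wording difference is that SAP 4.9 refers to infants who require the procedure, and 8.24 to infants who receive a therapy.

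**Step 2. Follow one infant.** Take an infant whose total bilirubin never exceeds 16.0 mg/dL, who receives phototherapy and has no transfusion. Under 8.24 this is a case. In the SAP 4.6 table the infant is counted. In SAP Tables 10 and 11 the infant is a non-case.

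**Step 3. Size per infant.** The documents give no phototherapy rate and no genotyping uptake (genotyping is optional under protocol 3.2), so the number reclassified cannot be computed. What can be given is the shift in the tabulated rate per therapy-only infant, if every infant is genotyped. Accrual is from SAP section 2, and the minimum of 8 RAL-exposed infants is from protocol 8.4.

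- Cohort 1: 10 + 6 = 16 infants; 1/16 = 6.25 percentage points.
- Cohort 2 RAL-naïve: 26 infants; 1/26 = 3.8 points.
- All of Cohort 2: 26 + 8 = 34 infants; 1/34 = 2.9 points.

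With fewer infants genotyped, each shift is larger.

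**Step 4. Direction of the effect on the test.** Assume two genotype groups, with about 30% of infants in the group where the cases fall: g = 5 of 16, 8 of 26, 10 of 34. These splits are assumptions; the documents give none. In each table below the opposite tail is more probable than the observed result, so the two-sided Fisher p equals the one tail.

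With k cases all in the group, p = C(g,k)/C(N,k). With three cases in the group and one outside it, p = [C(g,3)(N−g) + C(g,4)]/C(N,4).

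| N (g) | 2 in group | 3 in group | 3 in group, 1 outside |
|---|---|---|---|
| 16 (5) | 10/120 = 0.083 | 10/560 = 0.018 | 115/1820 = 0.063 |
| 26 (8) | 28/325 = 0.086 | 56/2600 = 0.022 | 1078/14950 = 0.072 |
| 34 (10) | 45/561 = 0.080 | 120/5984 = 0.020 | 3090/46376 = 0.067 |

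From the first column to the second, a restored therapy-only case falls in the same group and p drops. From the second to the third, it falls in the other group and p rises. Which happens depends on data not yet seen, so the wider definition cannot be recommended on grounds of power.

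**The case against.** **The narrow definition may be deliberate.** Bilirubin above 16.0 mg/dL or an exchange transfusion is the pair of events at which protocol 6.13 gives no further raltegravir, and 7.2 names the same two for expedited reporting. Someone could have chosen that pair as the more severe outcome, less dependent on local treatment habits. This stands as a possible explanation. But the SAP does not state it, and the V3.0 entry in its revision history mentions the mock-up tables for this analysis, not a change of definition. The unused therapy fields suggest a slip but do not prove one.

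**Timing.** SAP V3.0 is dated 3 January 2017 and says that "Protocol Version 2.0 is currently being drafted and if approved, will open accrual to Cohort 2 RAL exposed group". Protocol Version 2.0 is dated 18 January 2017. The Version 1.0 text of 8.24 is not available, so SAP 4.9 may have matched the protocol then in force. This also stands. It bears on how the mismatch arose, not on whether the current documents agree.

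**Is the SAP contradicting itself?** A reader might infer so from 4.6 and 4.9. That is too strong. SAP 4.6 describes a safety table and does not label its composite as a definition of hyperbilirubinemia; SAP 4.9 defines a response variable for another purpose. The two differ without explanation, but the firm comparison is with 8.24, which does define the term.

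**Does the narrow definition cost power?** A reader might infer this too, since fewer cases usually means less information. Step 4 shows that it does not follow. Phototherapy is given by local standards, so therapy-only cases may fall in either genotype group. The SAP already calls the power of these tests extremely limited.

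**Neighbouring points.** A reader might add that the pooled UGT1A1 mutation group breaches the *28/*28 objective, that the logistic model of protocol 8.711 is missing from the SAP, or that SLCO1B1 appears where SLCO1B3 is meant. None is a clear error. Protocol 8.711 can be read as allowing the any-polymorphism split, and Table 10 already gives (TA)7(TA)7 its own column and an all-genotype test. The logistic model is conditional in 8.711. SLCO1B1 may be an intended second gene, since reference 64 of the protocol names both.

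**Conclusion.** The mismatch is real and holds on the text alone: two of the four components of the protocol's outcome are absent from SAP 4.9, with no reason given. If the SAP is followed as written, any genotyped infant who qualifies by phototherapy or another therapy alone goes in the wrong row of Tables 10 and 11 relative to protocol 8.24. The argument is conformity with the protocol's defined outcome.

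The size is unknown. It is zero if no genotyped infant qualifies by therapy alone, and otherwise follows the per-infant shifts in Step 3, which assume complete genotyping. The documents do not support a claim of lost power, of a definite departure from the protocol version in force when the SAP was written, or of a mistake rather than an unstated choice.

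Severity is minor. The analysis is secondary and low-powered, and neither the primary safety endpoint nor the dose-finding safety guidelines use this variable.

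**What to change.** In SAP 4.9, replace the definition with that of protocol 8.24 for Tables 10 and 11 and their Cohort 2 versions. Keep bilirubin above 16.0 mg/dL or exchange transfusion as a named sensitivity analysis. If the narrow pair was chosen on purpose, state the reason beside it.

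The cost is a change of SAP wording and one repeat of the tables. The phototherapy and other-therapy fields are already in the SAP 4.9 data line, so no new data collection or sample is needed. The cells will stay small.

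Optional housekeeping in the same edit: state which listed genotype is *28/*28, and reconcile SLCO1B1 (protocol 3.2 and footnote 11 of Appendices II-A and II-B) with SLCO1B3 (protocol 1.27, 2.22, 8.24, 8.711 and SAP 4.9) by saying whether one or both genes are typed.
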